Table Appendix-9.	Participant Grouping for Immunogenicity Analyses of Anti-GS-2872.....	73
Table Appendix-10.	Participant Grouping for Immunogenicity Analyses of Both Anti-GS-5423 and Anti-GS-2872	73

LIST OF IN-TEXT FIGURES

Figure 1-1.	Study Schema	11
-------------	--------------------	----

LIST OF ABBREVIATIONS

ADA	antidrug antibody
AE	adverse event
ALT	alanine aminotransferase
AQL	above quantitation limit
ART	antiretroviral therapy
ARV	Antiretroviral
AST	aspartate aminotransferase
BE	bioequivalence
B/F/TAF	bictegravir/emtricitabine/ tenofovir alafenamide, Biktarvy®
BIC	bictegravir, B, GS-9883
BLQ	below the limit of quantitation
BMI	body mass index
bNAbs	Broadly Neutralizing Antibodies
CFR	Code of Federal Regulations
CI	confidence interval
CRF	case report form
CSR	clinical study report
CTCAE	Common Toxicity Criteria for Adverse Events
DMC	data monitoring committee
ECG	electrocardiogram
ET	early termination
EVG	elvitegravir, E
FAS	Full analysis set
FDC	fixed dose combination
FTC	emtricitabine
Gilead	Gilead Sciences
GDRC	Gilead Data Review Committee
GLSM	geometric least-squares mean
Hb	hemoglobin
IV	intravenous
LA	Long-acting
ICH	International Conference on Harmonization (of Technical Requirements for Registration of Pharmaceuticals for Human Use)
LLOQ	lower limit of quantitation
MedDRA	Medical Dictionary for Regulatory Activities
MST	Medical Surveillance Team
PK	pharmacokinetic
POC	proof of concept
PP	per protocol

PT	preferred term
Q1, Q3	first quartile, third quartile
SAP	statistical analysis plan
SC	subcutaneous
SD	standard deviation
SI	International System of Units (Système International d'Unités)
SOC	system organ class
TAF	tenofovir alafenamide
TEAE	treatment-emergent adverse event
TFLs	tables, figures, and listings
TFV-DP	tenofovir diphosphate
ULOQ	upper limit of quantification
ULN	upper limit of normal
VF	virologic failure
VR	ventricular rate
WHO	World Health Organization

PHARMACOKINETIC ABBREVIATIONS

λ_z	terminal elimination rate constant, estimated by linear regression of the terminal elimination phase of the log plasma/serum concentration of drug versus time curve of the drug
%AUC _{exp}	percentage of AUC extrapolated between AUC _{last} and AUC _{inf}
AUC _{inf}	area under the concentration versus time curve extrapolated to infinite time
AUC _{last}	area under the plasma/serum concentration versus time curve from time zero to the last quantifiable concentration
AUC _{0-26wk}	area under the plasma/serum concentration versus time curve from time zero to week 26
CL	clearance
C _{26wk}	Plasma/serum concentration of drug at Week 26
C _{max}	maximum observed plasma/serum concentration of drug
C _{max day1}	maximum observed plasma/serum concentration of drug at Day 1
t _{1/2}	estimate of the apparent terminal half-life of the drug in plasma/serum, calculated by dividing the natural log of 2 by the terminal elimination rate constant (λ_z)
T _{last}	time (observed time point) of last observed quantifiable plasma/serum concentration of drug
T _{max}	time (observed time point) of C _{max}
T _{max day1}	time (observed time point) of C _{max day1}
V _{ss}	volume of distribution at steady state

1. INTRODUCTION

This statistical analysis plan (SAP) describes the statistical analysis methods and data presentations to be used in tables, figures, and listings (TFLs) in the clinical study report (CSR) for the final analyses of Study GS-US-536-5816. This SAP is based on the study Protocol Amendment 2 dated 30 March 2022 and the electronic case report form (eCRF). The SAP will be finalized prior to database finalization. Any changes made after finalization of the SAP will be documented in the CSR.

1.1. Study Objectives

The primary objective of this study is as follows:

- To evaluate the safety and tolerability of a combination of the bNAbS GS-5423 and GS-2872 in combination with the HIV capsid inhibitor lenacapavir (LEN; GS-6207)

The secondary objectives of this study are as follows:

- To evaluate efficacy of the study regimens determined by the proportion of participants maintaining virologic suppression (HIV-1 RNA < 50 copies/mL) at Week 26
- To evaluate the pharmacokinetics (PK) of GS-5423, GS-2872, and LEN
- To evaluate immunogenicity of GS-5423 and GS-2872
- To evaluate the emergence of resistance to the components of the study regimens

[figure not shown]
1.2. Study Design

1.2.1. Design Configuration and Participant Population

This is a randomized, blinded, proof of concept (POC) Phase 1b study to evaluate the safety and efficacy of a single dose each of long-acting (LA) regimen of LEN, GS-5423, and GS-2872 in adults with HIV-1 infection who are virologically suppressed on oral antiretroviral therapy (ART).

An overview of the study design is described below and shown in [Figure 1-1](#).

Figure 1-1. Study Schema

ART – antiretroviral therapy; ET – early termination; LEN – lenacapavir; PK – pharmacokinetic(s); SC – subcutaneous.

CCI

Participants in the Primary Cohort and in the optional **Pilot Cohort** will be randomized in a 1:1 ratio to one of the following 2 treatment groups based on the dose of GS-2872 as in Section 1.2.2.

1.2.2. Treatment Groups

Treatment Group 1:

Oral LEN for loading 600 mg followed by LEN 927 mg subcutaneous (SC) on Day 1; oral LEN for loading 600 mg on Day 2

GS-5423 30 mg/kg, administered via intravenous (IV) infusion over 60 minutes on Day 1 (after LEN SC injection)

GS-2872 10 mg/kg, administered via IV infusion over 60 minutes on Day 1 (after GS-5423 infusion).

Treatment Group 2:

Oral LEN for loading 600 mg followed by LEN 927 mg SC on Day 1; oral LEN for loading 600 mg on Day 2

GS-5423 30 mg/kg, administered via IV infusion over 60 minutes on Day 1 (after LEN SC injection)

GS-2872 30 mg/kg, administered via IV infusion over 60 minutes on Day 1 (after GS-5423 infusion).

There is no stratification for randomization for the Primary Cohort. For the optional Pilot Cohort, randomization will be stratified by the antibody (GS-5423 or GS-2872) to which the participant is sensitive.

All participants will discontinue their background oral antiretroviral (ARV) regimen 1 day prior to receiving study drugs on Day 1.

At Week 26, all participants will resume their baseline regimen of once daily oral ART (or compatible regimen selected by the investigator) and return to the clinic for visits at Weeks 38 and 52.

Accordingly, efficacy and safety analyses will be conducted on CCI

CCI

CCI

Details of these two analysis periods will be addressed later in Section 3.

Unblinded treatment assignments will be provided to the investigators after all participants are back on their baseline ARVs (or compatible regimen selected by the investigator) at Week 26 or have discontinued the study, and the Week 26 analysis has been completed.

1.2.3. Key Eligibility Criteria

HIV-1 infected participants who meet the following criteria:

- Age between 18 and 65 years at screening
- On first-line ART for ≥ 2 years prior to screening. A change in ART regimen ≥ 28 days prior to screening for reasons other than virologic failure (VF) (eg, tolerability, simplification, drug-drug interaction profile) is allowed
- No documented historical resistance to the current ART regimen
- Plasma HIV-1 RNA < 50 copies/mL at screening

- Documented plasma HIV-1 RNA < 50 copies/mL for ≥ 18 months preceding the screening visit (or undetectable HIV-1 RNA level according to the local assay being used if the limit of detection is ≥ 50 copies/mL). Unconfirmed virologic elevations of ≥ 50 copies/mL (transient detectable viremia, or “blip”) prior to screening are acceptable.
- Proviral phenotypic sensitivity to both GS-5423 and GS-2872 at screening by the PhenoSense monoclonal antibody (mAb) Assay (Monogram Biosciences) for inclusion in the **Primary Cohort**; sensitivity at screening by the PhenoSense mAb Assay (Monogram Biosciences) to 1 mAb, either GS-5423 or GS-2872, **CC1** prior to enrollment for inclusion in the optional **Pilot Cohort**
 - In both cohorts, GS-5423 sensitivity is defined as 90% inhibitory concentration (IC_{90}) ≤ 2 μ g/mL; GS-2872 sensitivity is defined as $IC_{90} \leq 2$ μ g/mL
- CD4+ count nadir ≥ 350 cells/ μ L
- Screening CD4+ count ≥ 500 cells/ μ L
- Availability of a fully active alternative ART regimen, in the opinion of the investigator, in the event of discontinuation of the current ART regimen with development of resistance
- No comorbid condition requiring ongoing immunosuppression
- No evidence of current hepatitis B virus (HBV) infection
- No evidence of current hepatitis C virus (HCV) infection (prior infection cleared spontaneously or with treatment is acceptable)
- No history of opportunistic infection or illness indicative of Stage 3 HIV disease

1.2.4. Duration of Treatment

Duration of study drug treatment is approximately 26 weeks.

1.2.5. Study Procedures/Frequency

1.2.5.1. Screening

Due to the extended laboratory processing time for bNAb sensitivity testing, screening procedures for the Primary Cohort will be conducted in two parts. For the optional Pilot Cohort, participants will be selected from the previously screened/failed participants in the Primary Cohort and will directly proceed to Screening Part 2 (no need to repeat Screening Part 1).

Screening Part 1: Assessment of medical history, adverse events (AEs), and concomitant medications will be performed. A blood sample to assess for bNAb sensitivity will be collected and analyzed to support eligibility and entry into Screening Part 2.

Screening Part 2: Participants with proviral phenotypic sensitivity to either or both GS-5423 and GS-2872 will have the following assessments performed: changes in medical history, complete physical examination, vital signs, height, weight, electrocardiogram (ECG), and sample collection for laboratory analyses (hematology, chemistry, coagulation, thyroid function, urinalysis, serum pregnancy test [for women of childbearing potential], serum follicle-stimulating hormone [FSH], HIV-1 RNA, CD4+ cell count, CD8+ cell count, CD4/CD8 ratio, HBV and HCV serologies, and estimated glomerular filtration rate [eGFR]). Laboratory samples for proviral DNA genotype and bulk viral outgrowth phenotype will be collected at screening for subsequent testing.

1.2.5.2. Randomization

Participants in the Primary Cohort who meet all eligibility criteria will be randomized in a 1:1 ratio to Treatment Group 1 or Treatment Group 2. Participants in the Pilot Cohort who meet all eligibility criteria will be randomized in a 1:1 ratio to Treatment Group 1 or Treatment Group 2. Participants in both cohorts will return to the clinic within 28 days after the Screening Part 2 visit for the Day 1 visit.

There is no stratification for randomization for the Primary Cohort.

For the optional Pilot Cohort, randomization will be stratified by the antibody (GS-5423 or GS-2872) to which the participant is sensitive.

1.2.5.3. Schedule of Assessments

Study drug(s) will be administered in-clinic on Day 1 and self-administered on Day 2 (note: administered in-clinic on Day 2 if participating in the CCI [REDACTED]). Participants will return for study visits on Weeks 4, 8, 12, 16, 20, 24, 26, 38, and 52 for study assessments.

Clinical and laboratory assessments including hematology, chemistry, urinalysis, pregnancy test (for women of childbearing potential), HIV-1 RNA, CD4+ cell count, CD8+ cell count, CD4/CD8 ratio, vital signs, weight, focused physical examination, eGFR, and assessment of AEs and concomitant medications will be performed at Day 1, Weeks 4, 12, 26, 38, 52, early termination (ET), and post-ET follow-up visits (note: complete physical examination will be performed at Day 1 and ET).

Thyroid will be assessed at screening, Day 1, Weeks 4, 12, 26, 38, and 52.

ECG will be performed at screening, Day 1, Weeks 26, and 52.

HIV-1 RNA will also be assessed at Weeks 4, 8, 12, 16, 20, 24, 26, 38, and 52.

CCI [REDACTED]

CCI [REDACTED]

Plasma storage sample for virology testing at all visits except screening and Days 2 and 8.

Serum samples for immunogenicity assessment (antidrug antibody [ADA]) will be collected at Day 1 (predose) and Weeks 4, 12, 26, 38, and 52.

During the study, combination ART consisting of the baseline regimen (or a compatible regimen selected by the investigator) will be restarted in any participant who meets criteria for VF (HIV-1 RNA \geq 200 copies/mL that is confirmed upon repeat testing or has HIV-1 RNA \geq 200 copies/mL at study drug discontinuation).

Pharmacodynamic biomarkers: CCI

CCI

CCI Fc-gamma receptor (FcγR) single nucleotide polymorphisms (SNP) will be evaluated using samples collected at the Day 1 visit (CCI analysis).

CCI If participants provide consent, a sample will be collected at the Day 1 visit but may be collected at any time during the study or at a separate study visit, if necessary.

Study procedures table can be found in [Appendix 1](#).

1.3. Sample Size and Power

Although the sample size in this study is determined based on practical considerations and past experience with similar types of studies, assuming the 2 treatment groups have a similar virologic suppression rate, a total of 20 participants in the Primary Cohort will provide at least 35%, the power to show the lower bound of 95% CI for Week 26 virologic response rate (HIV-1 RNA < 50 copies/mL as defined by the United States (US) Food and Drug Administration (FDA)-defined snapshot algorithm {[U. S. Department of Health and Human Services 2015](#)}) is greater than 83%. It was assumed that the virologic response rate at Week 26 was 95% (based on Gilead studies GS-US-380-1844 and GS-US-380-4030), 12% was a clinically tolerable margin for Phase 1b studies, and a one-sided exact test with a significance level 0.025 was used. The sample size and power calculations were made using the statistical software package PASS (Version 14, NCSS, LLC; Kaysville, Utah, USA).

The estimated 95% CI for possible range of VF rate is provided in [Table 1-1](#). For example, with 1 VF event occurrence (5% estimated VF rate), a sample size of 20 participants can provide 95% confidence that the true VF rate is unlikely to be higher than 24.9%.

Table 1-1. Estimated Virologic Failure Rate and its 95% CIs (from the Clopper-Pearson Exact CI) Based on Number of Virologic Failure Event in Each Group or in Total

Sample Size	20				
Number of VF Events	0	1	2	3	4
Estimate of Incidence of VF (%)	0.0	5.0	10.0	15.0	20.0
Lower Bound of 95% CI (%)	0.0	0.1	1.2	3.2	5.7
Upper Bound of 95% CI (%)	16.8	24.9	31.7	37.9	43.7

VF = virologic failure.

Software: PASS® Version 14 (NCSS LLC, Kaysville, Utah, USA)

A total of approximately 20 participants in the Primary Cohort will provide reasonable assessment of safety and the descriptive PK profile throughout the study. A total of up to 20 participants in the optional Pilot Cohort is based on practical considerations.

2. TYPE OF PLANNED ANALYSIS

2.1. Interim Analysis

Prior to the final analysis, interim analyses have been completed. The results from these analyses may be submitted to scientific meetings and for publications and to regulatory agencies to seek guidance for the overall clinical development program.

2.1.1. Gilead Data Review Committee Analysis

The GDRC reviewed the progress, unblinded safety and efficacy data of this study. The GDRC convened after all participants enrolled in the Primary Cohort had completed their Week 12 visit or prematurely discontinued from the study.

No formal stopping rules was used by the GDRC for safety outcomes. Rather, a clinical assessment was made to determine if the nature, frequency, and severity of AEs associated with a study regimen warrant the early termination of the study in the best interest of the participants. Based on safety and preliminary efficacy, the GDRC determined that the optional Pilot Cohort would be implemented.

2.2. Primary Analysis

The unblinded primary analysis was conducted after all participants in the Primary Cohort had completed Week 26 visit or prematurely discontinued from the study.

2.4. Final Analysis

The final analysis will be performed after all participants have completed the study or prematurely discontinued from the study, outstanding data queries have been resolved or adjudicated as unresolvable, and the data have been cleaned and finalized. The final analysis will include data from the Primary Cohort and the Pilot Cohort. This document describes the analysis plan for the Final Analysis.

3. GENERAL CONSIDERATIONS FOR DATA ANALYSES

Analysis results will be presented using descriptive statistics. For categorical variables, the number and percentage of participants in each category will be presented; for continuous variables, the number of participants (n), mean, standard deviation (SD) or standard error (SE), median, first quartile (Q1), third quartile (Q3), minimum, and maximum will be presented.

By-participant listings will be presented for all participants in the All Randomized Analysis Set and sorted by participant identification (ID) number, visit date, and time (if applicable). Data collected on log forms, such as AEs, will be presented in chronological order within the participant. The treatment group to which participants were randomized will be used in the listings. Age, sex at birth, race, and ethnicity will be included in the listings, as space permits.

There are the following 2 sets of analyses defined for this study. Data included in each analysis are defined as follows:

Long Acting (LA) Regimen Period Analysis

Long-acting (LA) Regimen Period Analysis includes efficacy (ie, HIV-1 RNA and CD4 cell count and percentage) and safety data collected during **Long Acting Regimen Period** from participants randomized and received at least one dose of the complete long acting study drug regimen (ie, SC LEN + GS-5423 and GS-2872) up to ART restart (eg, Week 26). All data collected up to the last exposure date of LA regimen (defined in Section 3.8.1) will be summarized except for data on AEs, death and concomitant medications. For AEs, death and concomitant medications, only data collected prior to the last exposure date of LA regimen will be included. For participants who did not restart ART on or before last study date or have missing ARV restart date, all data will be included.

Data included in this analysis will be used to assess the efficacy and safety data collected during the LA regimen period of the study. Results will be summarized by treatment group and overall.

Whole Study Period Analysis

Whole Study Period Analysis includes efficacy (ie, HIV-1 RNA and CD4 cell count and percentage) and safety data collected during **Whole Study Period** from participants randomized and received at least one dose of study drug up to the end of the study (eg, Week 52). For efficacy summary, all HIV-1 RNA and CD4 data during the whole study will be included. For safety summary, all safety data collected up to the last exposure date (defined in Section 3.8.1) from participants who prematurely discontinued study or completed study will be included.

Data included in this analysis will be used to assess the efficacy and safety data collected during the study. Results will be summarized by treatment group and overall.

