6.8.2. Virologic Failure

Participants who meet the criteria listed below will be considered to have VF:

- Participants with HIV-1 RNA ≥ 200 copies/mL on 2 consecutive visits will be considered to have VF. The blood sample from the confirmation visit will be the primary sample used for HIV-1 genotypic and phenotypic testing of capsid and env for study drugs (LEN, GS-5423, and GS-2872) and genotypic testing of RT, PI, and/or IN genes for the baseline ART regimen. Samples collected at baseline will be used for comparison of genotypic and phenotypic testing of study drugs at VF. The participant will be restarted on their baseline ART regimen (or compatible regimen selected by the investigator) and continue on study follow-up but will not receive additional doses of the study regimen. Participants will return for an unscheduled visit, 4 weeks after restarting their baseline ART regimen (or compatible regimen selected by the investigator) to confirm virologic suppression.
- Participants with HIV-1 RNA ≥ 200 copies/mL at study discontinuation or Week 26 will be considered to have VF. The blood sample from the last visit or Week 26 with HIV-1 RNA ≥ 200 (ie, not confirmable) will be the primary sample used for HIV-1 genotypic and phenotypic testing. The participant will be restarted on their baseline ART regimen (or compatible regimen selected by the investigator) and continue on study follow-up but will not receive additional doses of the study regimen. Participants will return for a unscheduled visit 4 weeks after restarting their baseline ART regimen (or compatible regimen selected by the investigator) to confirm virologic suppression.
- Participants with ongoing HIV-1 RNA ≥ 50 copies/mL but who do not meet criteria for VF must be discussed with the medical monitor.

For participants who are off study drug but remain on study, it will be the investigator's discretion to manage VR.

Figure 6-1. Virologic Rebound Schema

VF = virologic failure

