3.8.1. Definition of Key Dates and Study Day

Study Day 1 is defined as the day when the first dose of any study drug was taken, as recorded on the Study Drug Administration eCRF (ie, oral LEN, SC LEN or infusion drugs [GS-5423, GS-2872]).

Last Dose Date is defined as the latest dose date of any study drug as recorded on the Study Drug Administration eCRF (ie, oral LEN, SC LEN or infusion drugs (GS-5423, GS-2872) for participants who prematurely discontinued study drug or completed study drug according to Study Drug Completion eCRF.

Study Days are calculated relative to Study Day 1 of study drug and derived as follows:

- For postdose study days: Assessment Date – First Dose Date + 1
- For days prior to the first dose: Assessment Date – First Dose Date

Baseline Value is defined as the last value obtained on or prior to the first dose of study drug.

Last Study Date is the latest clinic visit dates, and/or the laboratory visit dates, whichever is latest, including the any follow-up visit dates, for participants who prematurely discontinued study or completed study according to the Study Completion eCRF.

Last Exposure Date is defined as follows for participants who prematurely discontinued study or complete study according to Study Completion eCRF (i.e. participant answered “No” or “Yes” for “Did the participant complete the protocol-planned duration of the study” on Study Completion form):

- For participants who receive any injection or infusion, last exposure date is defined as last study date.
- For participants who do not receive any injection or infusion (i.e. for those who only receive oral LEN), last exposure date is defined as the earliest of the last dose date plus 60 days and the last study date.

The last exposure date is defined considering the prolonged exposure of LEN, GS-5423, and GS-2872 after the last dose date of LEN, GS-5423, and GS-2872 through the end of study.

Last Exposure Date of LA Regimen is defined as follows for participants who prematurely discontinued study drug or complete study drug according to Study Drug Completion eCRF (i.e. participant answered “No” or “Yes” for “Did participant complete study drug dosing as specified per protocol” on Study Drug Completion form):

- the earliest date of last study day or ART restart day for participants who prematurely discontinued study or complete study, or

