- the ART restart date for participants who were still on study. If the ART restart date is missing, the data cut date will be used to impute the last exposure date for participants who are still on study at the time of the data cut date.

The last exposure date of LA regimen is defined considering the prolonged exposure of LEN, GS-5423, and GS-2872 after the last dose date of LEN, GS-5423, and GS-2872 through the ART restart date.

ART Restart Date is defined as the date when ART is resumed.

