6.1.2. FDA-defined Snapshot Algorithm

The analysis window at Week 26 is defined as from Study Day 176 to Study Day 224, inclusive. All HIV-1 RNA data collected on-treatment (ie, data collected up to the earliest date of (196 days [28 weeks] after the dose date of complete long acting regimen, date of restarting ART) will be used in the US FDA-defined snapshot algorithm {[U. S. Department of Health and Human Services 2015](#)}. Virologic outcome will be defined as the following categories:

- HIV-1 RNA < 50 copies/mL: this includes participants who have the last available on-treatment HIV-1 RNA < 50 copies/mL in the Week 26 analysis window
- HIV-1 RNA ≥ 50 copies/mL: this includes participants
 - a) Who have the last available on-treatment HIV-1 RNA ≥ 50 copies/mL in the Week 26 analysis window, or
 - b) Who do not have on-treatment HIV-1 RNA data in the Week 26 analysis window and
 - i) discontinue study drug prior to or in the Week 26 analysis window due to lack of efficacy, or
 - ii) discontinue study drug prior to or in the Week 26 analysis window due to AE or death and have the last available on-treatment HIV-1 RNA ≥ 50 copies/mL, or
 - iii) discontinue study drug prior to or in the Week 26 analysis window due to reasons other than AE, death, or lack of efficacy and have the last available on-treatment HIV-1 RNA ≥ 50 copies/mL.

- No Virologic Data in the Week 26 Window: this includes participants who do not have on-treatment HIV-1 RNA data in the Week 26 analysis window because of the following:
 - a) Discontinuation of study drug prior to or in the Week 26 analysis window due to AE or death and the last available on-treatment HIV-1 RNA < 50 copies/mL, or
 - b) Discontinuation of study drug prior to or in the Week 26 analysis window due to reasons other than AE, death, or lack of efficacy and the last available on-treatment HIV-1 RNA < 50 copies/mL or,
 - c) Missing data during the window but on study drug.

The flowchart of the US FDA-defined snapshot algorithm is provided in [Appendix 2](#).

The Week 26 virologic outcomes for the US FDA-defined snapshot algorithm will be flagged in the listings.

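### A missing ART restart date is handled as if ART was never restarted, so data on resumed oral ART can enter the LA-period tables

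*SAP*

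**What the plan says.** SAP 3 defines the LA Regimen Period Analysis as running from dosing up to ART restart, with Week 26 as the example. It then adds: "For participants who did not restart ART on or before last study date or have missing ARV restart date, all data will be included".

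SAP 3.8.1 points the same way. For anyone who has completed or left the study, the last exposure date of the LA regimen is "the earliest date of last study day or ART restart day for participants who prematurely discontinued study or complete study, or". With no restart day, only the last study day remains. For participants still on study: "If the ART restart date is missing, the data cut date will be used to impute the last exposure date".

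Restart is part of the design. SAP 1.2.2: "At Week 26, all participants will resume their baseline regimen of once daily oral ART". After virologic failure it comes earlier. Protocol 6.8.2: "The participant will be restarted on their baseline ART regimen (or compatible regimen selected by the investigator) and continue on study follow-up".

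The snapshot is handled separately. SAP 6 takes the snapshot endpoints out of the LA and Whole Study split, and SAP 6.1.2 cuts on-treatment HIV-1 RNA at the "earliest date of (196 days [28 weeks] after the dose date of complete long acting regimen, date of restarting ART". It does not say what happens when the restart date is missing.

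**The concern.** The rule gives two different states the same treatment: ART not restarted, and ART restarted on an unknown date. In this design a participant who stays on study past Week 26, or who has confirmed virologic failure, is required to be back on ART. For such a participant a missing date most plausibly means that the date was not recorded.

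The LA period exists to separate the study regimen from background ART. If it runs on to the last study date, events on oral ART are reported as LA-regimen events. SAP 4.2.1 itself describes LA-period exposure as lasting up to 26 weeks. The primary endpoint is treatment-emergent SAEs through Week 26 (SAP 7). The LA-period SAE table is the natural place to read it, although the SAP does not name the table that delivers it.

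On efficacy, a participant rescued with oral ART before Week 26 could be shown as suppressed at Week 26 in an LA-period table. That error favours the study regimen.

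**Working it through.** The plan gives no figure for this rule, so the check is date arithmetic. The n = 20 used below comes from Protocol 8.10 and SAP 1.3. Their power statement reproduces: with an exact one-sided test at 0.025 against 83%, only 20/20 qualifies (0.83^20 = 0.0241; 19 or more gives 0.1227), and power at 95% is 0.95^20 = 0.358, in line with at least 35%.

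**Inputs**
- Week 26 = Day 182, Week 52 = Day 364; Week 26 HIV-1 RNA window Day 176 to 224 (SAP Table 3-2). The CD4 window also closes at Day 224 (Table 3-3).
- The latest HIV-1 RNA or CD4 record in a window is used (SAP 3.8.3).
- LA-period TEAEs and laboratory abnormalities are cut only at the last exposure date of the LA regimen, with no Week 26 cap (SAP 7.1.5.1, 7.2.2.1).
- LA-period HIV-1 RNA and CD4 tables stop at the Week 26 visit (SAP 6.1.3.3, 6.2.2.1).
- A first value of at least 200 copies/mL is retested within 2 to 3 weeks (Protocol 6.8.1).

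**Safety, scheduled restart, date missing.** 364 − 182 = 182 days = 26 weeks on ART enter the LA period. LA exposure becomes 364/7 = 52 weeks instead of 182/7 = 26.

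**Safety, early rescue, date missing.** Assume restart on the day of confirmation and a last study date of Day 364.
- First value at Week 4, restart on Day 28 + 14 = 42 or 28 + 21 = 49: (364 − 42)/7 = 46 or (364 − 49)/7 = 45 weeks.
- Restart on Day 56 + 21 = 77: (364 − 77)/7 = 41 weeks.
- Restart on Day 140 + 21 = 161: (364 − 161)/7 = 29 weeks.

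**HIV-1 RNA and CD4 tables.** After a scheduled restart, at most 224 − 182 = 42 days = 6 weeks. After a restart on Day 42, (224 − 42)/7 = 26 weeks.

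**Week 26 Missing = Failure, LA period.** Take one participant rescued before Day 176 and suppressed on ART by Week 26, with the other 19 below 50 copies/mL.
- Date known: the Week 26 value lies outside the LA period, is missing and counts as failure. 19/20 = 95%.
- Date missing: the on-ART value counts. 20/20 = 100%.

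The difference is 1/20 = 5 points whatever the others do, or 1/10 = 10 points in a group of 10.

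**Week 26 Missing = Excluded, LA period.** Date known: the participant leaves numerator and denominator, 19/19 = 100%. Date missing: 20/20 = 100%. With one other failure it is 18/19 = 94.7% against 19/20 = 95.0%.

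**Snapshot.** With a known restart before Day 176 there is no on-treatment value in the window, so the participant cannot be classed as below 50 copies/mL. If a missing date leaves only the 196-day limit (an assumption, since SAP 6.1.2 is silent), an on-ART value from Day 176 to Day 196 or 197 counts as on-treatment. That is 196 − 176 + 1 = 21 days, or 22 if the limit is read as Study Day 197.

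**The case against.** The best defence is that the case will be rare. A rescued participant has an extra visit 4 weeks after restart (Protocol 6.8.2), concomitant medications are reviewed at every visit (Protocol Appendix 2), non-study ARVs are listed (SAP 7.4.1), and queries are settled before the final analysis (SAP 2.4). This stands as a point about frequency. But SAP 2.4 also allows for queries that cannot be resolved, and the SAP wrote a rule for this very case, so the rule should give the right answer.

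The rule is also correct for some participants. Someone who leaves before restarting has no restart date, and the early termination visit offers counselling and referral rather than an observed restart (Protocol 6.5). Ending that participant's LA period at the last study date is right. A reader might infer that the rule fails whenever it is used; it does not.

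Four other stronger readings go too far:
- *The rule alters the snapshot endpoints.* SAP 6 excludes them from the LA-period analysis. A flip there rests on the silence of SAP 6.1.2.
- *One flip decides the trial against 83%.* The exact 95% lower limits, 83.2% for 20/20 and 75.1% for 19/20, do lie on either side of that mark. But 83% appears only in the sample-size rationale for the snapshot rate and is not a success criterion. The table that the rule can change is an other efficacy endpoint (SAP 6.2).
- *Missing = Excluded also turns a failure into a responder.* With the date known, the participant is excluded rather than failed, so the rate hardly moves.
- *The data-cut imputation adds to the problem.* It applies only to participants still on study, and there are none at the final analysis that this SAP covers.

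**Conclusion.** The concern holds in limited form. For a participant who did restart ART but whose date is missing, SAP 3 and 3.8.1 extend the LA period to the last study date. About 26 weeks of on-ART safety data then enter the LA-period tables after a scheduled restart, and about 29 to 46 weeks in the early-rescue examples, assuming restart at confirmation and follow-up to Day 364. HIV-1 RNA and CD4 tables take in at most 6 weeks after a scheduled restart. One rescued participant moves the Week 26 Missing = Failure rate by 5 points if n = 20.

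The same flip in the snapshot is possible but conditional: it needs the 196-day limit to be the only one left and a sample between Day 176 and about Day 196. A reader might also infer that the primary endpoint is contaminated. That follows only if it is read from the LA-period SAE table without a separate Week 26 limit, which the SAP does not state.

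The documents give no frequency, and it should be low. The point is worth correcting because the rule is explicit, gives a wrong result in the case described, and is cheap to change.

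**What to change.** In SAP 3 and 3.8.1:

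1. Keep the inclusion of all data only for participants with no restart documented or observed, including those who left the study before a restart.
2. For participants known to have restarted while on study, or required by the design to have done so, whose date is missing, impute the earlier of (a) the visit at which virologic failure was confirmed and ART restart instructed and (b) the Week 26 visit date, or Day 182 if that visit was missed. Keep the samples taken at that visit.
3. For a partial date, use the imputed visit date if it fits the recorded month and year; otherwise use the compatible date nearest to it. Do not default to the earliest compatible date. A Week 26 restart recorded by month only would become the 1st of that month, up to 30 days early, which can fall before Day 176 and discard a genuine Week 26 value.
4. Use the same date for LA exposure and for the snapshot cutoff in SAP 6.1.2 and Appendix 2. The same cutoff wording in SAP 3.1.3 should follow.

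The cost is a few SAP sentences and one derivation. The LA period may be slightly short for someone who restarted a little later than the imputed date. If the Week 26 visit was missed, a later sample taken before the true restart would also be lost.
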